### Research Question and Aims

#### Specific aims and Hypotheses:

##### **Specific Aim 1: Identify Innate Cell Transcriptomic Signatures Associated with Sex and Immune Response to Influenza Vaccines in the Elderly.** To do this we will:

- **Aim 1.1** Test the hypotheses that vaccine type (MF59Flu vs HDFlu) and/or sex are associated with variations in innate cell immune outcomes (e.g., APC activation phenotype and cytokine/chemokine secretion).
- **Aim 1.2** Test the hypothesis that the increased Ag dose in HDFlu results in greater activation/suppression of the innate genes/genesets previously associated with immune responses to SDFlu. We will also test the hypothesis that the MF59 adjuvant results in activation/suppression of additional specific innate genes/genesets compared to HDFlu (see Overview and Rationale of Specific Aim 1).
- **Aim 1.3** Test the hypothesis that innate immune cell transcriptomic signatures mediate the association of vaccine type (or sex) with innate cell immune outcomes.
- **Aim 1.4** Test the hypothesis that the innate cell immune outcomes and transcriptomic signatures from Aim 1.3 will predict markers of humoral immunity (HAI Ab and B cell ELISPOT response).

##### **Specific Aim 2: Identify CD4+ T Helper (Th) Cell Transcriptomic Signatures Associated with Sex and Immune Response to Influenza Vaccines in the Elderly.** To do this we will:

- **Aim 2.1** Test the hypotheses that vaccine type (MF59Flu vs HDFlu) and/or sex are associated with variations in Th cell immune outcomes (e.g., Th phenotype and cytokine production).
- **Aim 2.2** Test the hypothesis that the increased Ag dose in HDFlu results in greater activation/suppression of the Th cell genes/genesets previously associated with immune responses to SDFlu. We will also test the hypothesis that the MF59 adjuvant results in activation/suppression of additional specific genes/genesets in CD4+ Th cells compared to HDFlu (see Overview and Rationale of Specific Aim 2).
- **Aim 2.3** Test the hypothesis that Th cell transcriptomic signatures mediate the association of vaccine type (or sex) with Th cell immune outcomes.
- **Aim 2.4** Test the hypothesis that the Th cell immune outcomes and transcriptomic signatures from Aim 2.3 will predict markers of humoral immunity (HAI Ab and B cell ELISPOT response).

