### Data Analysis

#### Data Analysis Plan:

The planned analyses for Aims 1 and 2 will follow the same strategies, so for Aim 2 analyses we point out the differences needed to adapt the analyses for Aim 2.

**Aim 2.1 Test the hypotheses that vaccine type (MF59Flu vs HDFlu) or sex is associated with variations in Th cell immune outcomes:** The analysis plans for Aim 1.1 will be followed, but using the Th phenotype and cytokine production outcomes, evaluating change from Baseline to Days 8 and 28.

**Aim 2.2 Test the hypothesis that the expression of specific genes is associated with differences in Th cell immune outcomes:** Analyses will parallel those for Aim 1.2, but use differential Th cell-specific gene and miRNA expression (change from Baseline to Days 8 and 28) as independent variables to evaluate for their association with change in Th cell immune responses.

**Aim 2.3 Test the hypothesis that Th cell transcriptomic signatures mediate the association of vaccine type (or sex) with Th cell immune outcomes:** Analyses will parallel those described in Specific Aim 1.3.

**Aim 2.4 Test the hypothesis that Th cell immune outcomes and transcriptomic signatures from Aim 2.3 will predict markers of humoral immunity (HAI Ab and B cell ELISPOT response):** The analysis plans closely follow the mediation analyses described in Aim 1.4. We will test the hypothesis that Th immune response and their associated genes (Aim 2.3), predict humoral immunity (HAI Ab titer and B cell ELISPOT response) at Day 28. We will also test the hypothesis that additional genes mediate humoral immunity independently of Th responses. To achieve this, we will treat Th responses as adjusting covariates, using the regression model: By adjusting for Th response, we seek genes/genesets that are only associated with humoral immune response.

**Power:** See Specific Aim 1. We anticipate stronger signals in the transcriptomic data from purified CD4+ T cells compared to PBMCs. The increased signal to noise ratio will allow for detection of smaller effects.

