### Potential Limitations and Alternative Strategies for Aims 1 and 2.

False-positive associations will be controlled by our clearly defined analysis plan, the use of false-discovery rates to assess significance, and geneset/pathway analysis to maximize power and minimize false discovery. Statistical power to detect effects is driven by our sample size of 400 subjects, which is larger than most systems biology studies, including our prior study of SDFlu in older subjects where we and others were able to successfully identify transcriptomic signatures of vaccine response. Accumulation of information across multiple genes increases the percent of variability explained by the model and hence increases the likelihood of detecting effects. Our analysis approach will also test the association of each innate and Th cell immune response with the expression of all genes in a specified geneset using kernel methods. Advantages of kernel methods are the following: 1) they allow for correlations among the different genes in a geneset; 2) they are robust to when some genes are positively associated with a response, others are negatively associated with a response, and other genes in the geneset are not associated; 3) and they allow adjustment for covariates. Finally, we will evaluate data-driven genesets using WGCNA to group genes into biological modules, which is an approach we have successfully used (see Preliminary Data).

Separate mediation analyses will be performed for mRNA and miRNA. If we find both mRNA and miRNA to be separate mediators in our initial analyses, we will evaluate their joint effects as a pathway of mediators using techniques developed by VanderWeele. Other confounding factors (e.g., immunosenescence, underlying medical conditions, obesity, and CMV serostatus) will be evaluated in our analyses as potential confounders.

**Expected Results and Impact of Findings for Specific Aims 1 and 2.** Our publications and preliminary data indicate a high likelihood of identifying not only significant vaccine type-

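### Aims 1.4 and 2.4 test signatures as predictors of HAI and ELISPOT in the subjects who supplied the selection, and no validation step is described

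*Protocol*

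**What the plan says.** The protocol works in two stages. Aim 2.3 selects signatures on cell outcomes: "Test the hypothesis that Th cell transcriptomic signatures mediate the association of vaccine type (or sex) with Th cell immune outcomes". Aim 2.4 then carries those signatures, together with the Th outcomes, forward to HAI and ELISPOT, under the hypothesis that "transcriptomic signatures from Aim 2.3 will predict markers of humoral immunity". The Data Analysis Plan states the target as testing whether they "predict humoral immunity (HAI Ab titer and B cell ELISPOT response) at Day 28". Aims 1.3 and 1.4 do the same for innate cells.

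On method, the Data Analysis Plan says "The analysis plans closely follow the mediation analyses described in Aim 1.4", and more generally "The planned analyses for Aims 1 and 2 will follow the same strategies". The Aim 1 plans themselves are not in the available text.

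The same section adds a second search: "We will also test the hypothesis that additional genes mediate humoral immunity independently of Th responses". Here the Th response is a covariate: "By adjusting for Th response, we seek genes/genesets that are only associated with humoral immune response".

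Potential Limitations and Alternative Strategies lists the protections against false positives: a defined plan, false-discovery rates, and geneset methods (kernel tests, WGCNA). It also argues: "Accumulation of information across multiple genes increases the percent of variability explained by the model and hence increases the likelihood of detecting effects". The SAP covers randomization, assay layout, normalization and a Wilcoxon test of HAI change by vaccine. Neither document describes cross-validation, a split sample, a hold-out set or replication.

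**The concern.** Selecting genes on Th rather than on HAI looks like protection against circularity, but it is only partial. The study expects Th and HAI responses to be related. If they are, a gene whose sample correlation with Th is too high by chance tends to have a sample correlation with HAI that is off in the same direction. Testing the selected genes on HAI in the same people reuses that chance component. The search for additional genes is more exposed, because it selects on the humoral outcome itself.

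At stake is the word *predict*. The protocol expects these results to inform vaccine and adjuvant design. A signature that fits the 400 participants but not the next 400 would mislead that work.

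**Working it through.** **Inputs from the documents.** There are 400 vaccinated subjects aged 65 and older, with 10% over-recruitment (Subject Information), so about 400 × (1 − 0.10) = 360 are evaluable. The documents give no number of genes, FDR level, R², accuracy measure or power figure for Aims 1.4 and 2.4, so there is no stated figure to reproduce.

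**Assumptions.** 5,000 to 10,000 independent genes; correlation ρ between the Th outcome and HAI; Benjamini-Hochberg (BH) selection at 0.05 to 0.20; second-stage test at nominal 5%. All sizes below are simulation results under these settings.

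**1. The mechanism.** To isolate it, take n = 360 and 10,000 genes unrelated to anything, and force the 20 most correlated with Th into a model for HAI. The R² expected by chance is k/(n − 1) = 20/359 = 0.056.

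| ρ | In-sample R² | R² in new subjects |
|---|---|---|
| 0 | 0.054 | −0.059 |
| 0.3 | 0.086 | −0.082 |
| 0.5 | 0.138 | −0.111 |

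At ρ = 0 there is only ordinary overfit. The extra comes from selection and grows with ρ.

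**2. FDR selection, pure noise.** With BH selection at 0.05 to 0.20, a signature appears in 0% to 18% of datasets. In most there is nothing to carry forward.

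**3. FDR selection, some genes affect Th, none affect HAI.** Th and HAI are correlated at 0.3 to 0.5 for other reasons, with n = 360 and 5,000 genes. Genes now pass selection, and those that pass tend to be the ones whose link with Th was overestimated. The nominal 5% test on HAI rejects roughly 8% to 50% of the time. In-sample R² is about 0.01 to 0.03, and R² in new subjects is below zero.

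**4. FDR selection, genes act on HAI through Th.** With n = 400, 5,000 genes, BH at 0.05, and 10 genes explaining 40% of Th:

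| ρ | In-sample R² | R² in new subjects | Difference |
|---|---|---|---|
| 0.3 | 0.038 | 0.002 | 0.036 |
| 0.5 | 0.084 | 0.035 | 0.049 |

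Even when the signature is genuine, more than half of the in-sample R² is optimism.

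**5. Selection directly on HAI.** Forcing the 20 noise genes most correlated with HAI gives in-sample R² of 0.35 (n = 400, 5,000 genes) to 0.40 (n = 360, 10,000 genes), against −0.25 to −0.27 in new subjects. Retesting that set in the same subjects rejected every time, even with Th as a covariate. Forced selection makes this an upper illustration. An FDR-controlled search can still support a claim of association; a retest in the same subjects, or a variance explained, cannot be taken at face value.

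**6. The variance-explained sentence.** In-sample R² rises with unrelated genes: 50 of them give 50/359 = 0.139 at n = 360. A rise in that quantity is not in itself evidence of effects.

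**The case against.** **FDR control is planned.** This stands in part. Step 2 shows that it largely prevents a signature arising from pure noise. It does not restore the second-stage test in step 3 or make R² honest in step 4.

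**Adjusting for Th removes the selection effect.** With noise genes it does: rejection returned to about 0.03 to 0.06. But the protocol states that adjustment only for the search for additional genes, not for the Aim 2.3 signatures. Nor is it dependable. When Th and HAI share other causes, conditioning on Th links the Th genes to HAI, and rejection rose as high as 0.9 to 1.0. That is a problem of interpretation which cross-validation does not cure, so the covariate cannot serve as the safeguard.

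**No R² is a planned result.** This stands. Variance explained appears only in an argument about power, and Aims 1.4 and 2.4 are worded as hypothesis tests. The criticism is that an R² would be inflated if reported without validation.

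**The Aim 1.4 plan is missing from the text.** This also stands. One can say that no validation is described, not that none was intended.

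**A stronger reading is tempting.** A reader might infer that the nominal 5% test is wrong 38% to 98% of the time with genes unrelated to anything. Those rates do arise at n = 360 with 5,000 noise genes: 0.42 (20 genes) and 0.375 (50 genes) at ρ = 0.3, and 0.96 and 0.98 at ρ = 0.5. They require forcing the top 20 or 50 genes through and testing them without Th. The documents do not support that reading: they name FDR as the criterion, and no section describes that unadjusted joint test.

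**Conclusion.** The point holds in a limited form. Signatures are selected and then tested as predictors in one cohort, a further search is made on the humoral outcome itself, and the available documents describe nothing that would show performance in new subjects. With FDR selection, the excess is a rejection rate of roughly 8% to 50% at nominal 5% when some genes affect Th and none affect HAI, with small in-sample R² values that vanish in new subjects. These sizes depend on the assumed FDR level, gene count, Th-HAI correlation and independence of genes; correlated genes would change them, and at zero Th-HAI correlation the selection effect disappears.

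The SAP's primary Wilcoxon comparison of HAI change by vaccine uses no signatures and is unaffected. This is a correction to the mechanistic aims, worth making before those data are analysed.

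**What to change.** For Aims 1.4 and 2.4, and for the search for additional genes, specify repeated K-fold cross-validation in which filtering, the Aim 1.3 or 2.3 selection and the model fit are all repeated inside each fold. Base any claim of prediction on out-of-fold R², with a permutation p-value obtained by rerunning the whole procedure. Label all other results as associations. State the FDR level, and whether the Aim 2.3 signatures are tested with or without the Th response in the model.

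In Potential Limitations and Alternative Strategies, amend the sentence on variability explained to say that only cross-validated variance explained will support a claim of prediction. If the Aim 1.4 plan already contains a validation step, bring it into the protocol or SAP.

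The cost is analysis time, and the reported effects will be smaller. No extra subjects, samples or assays are needed.

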#### Background:

**Scientific Premise of the Proposed Research.** While older populations are at the highest health risk from seasonal influenza, these populations have poor immune responses to standard-dose seasonal influenza vaccine (SDFlu). Our study is focused on two influenza vaccines for use in subjects  $\geq 65$  years of age: **MF59Flu**, an adjuvanted subunit vaccine (licensed in late 2015); and **HDFlu**, a split-virus vaccine containing 4x the hemagglutinin protein (licensed in 2009). These vaccines have demonstrated greater immunogenicity than SDFlu in older populations, but little is known about the underlying mechanisms. **For these two vaccines, systems biology studies designed to identify the mechanisms for improved immune response have never been conducted in older individuals, nor have sex-based differences been adequately studied.** The goals of this proposed project are to examine inter-individual variations in innate and T helper (Th) responses, and identify *transcriptomic signatures* associated with immune responses (including correlates of protective immunity) to influenza vaccines in older individuals.

**This is important for the following reasons:**

**A. Public Health Importance.** Seasonal influenza A is believed to kill between 3,000–49,000 annually, resulting in over 250,000 excess hospitalizations and annual costs of  $>\$90$  billion in the US. Influenza morbidity and mortality increase significantly with age. **More than 90% of influenza-associated deaths occur in individuals  $\geq 65$  years of age, and are predominantly associated with influenza A/H3N2.** During the 2014–2015 influenza season, adults age  $\geq 65$  years had an influenza-related hospitalization rate of 314 per 100,000 people—a record high since surveillance began in 2005. The efficacy of influenza vaccines is diminished in older adults and varies widely (15% to 75%), averaging  $<50\%$ . Considering the unprecedented population growth in persons  $\geq 65$  years of age and the significant public health impact of influenza, **it is imperative that influenza vaccine-induced immunity in older adults be better understood.** Due to increased mortality in the elderly and cognizant of budgetary limitations, we will focus on influenza A/H3N2.

**B. Knowledge Gap—Immune Response Differences to Adjuvanted vs. High-Dose Influenza Vaccines.**

HDFlu contains 60ug HA per influenza strain, and has been the focus of high-quality studies, including a study of 31,989 older individuals ( $\geq 65$  years of age) that demonstrated higher immunogenicity (ratio of GMT 1.8) and 24% greater protection against influenza illness than SDFlu (15ug HA/strain/dose). MF59Flu also induces higher immunogenicity and longer persistence of Ab titers than non-adjuvanted SDFlu. A recent large study in 7,082 individuals ( $\geq 65$  years of age) demonstrated significantly higher immunogenicity ( $p < 0.001$ , seroconversion and HAI GMT) of MF59Flu vaccine compared to SDFlu (particularly against A/H3N2). A single small systems biology study comparing MF59Flu and SDFlu in immunoimmature children (14- to 24-months-old, n=90) identified significantly higher transcriptional responses to MF59Flu and identified early innate response signatures correlated with Day 28 Ab titers. These include M16 (a module associated with TLR and inflammatory signaling); M11 (a module regulating monocyte function); M75 (a module controlling IFN-induced antiviral response); M156 (a module associated with Ab secreting cells); and S3 (a module with genes involved in immunoglobulin production). These genesets and those identified in other systems biology studies of influenza vaccine response will be evaluated for their influence on immune responses to MF59Flu and HDFlu in this proposal.

**The underlying immunologic mechanisms for the improved immunogenicity of MF59Flu and HDFlu are largely unknown for older adults. Our proposal will answer key questions (as illustrated in Figure 1) regarding innate and Th immune responses to these vaccines, the underlying transcriptomic signatures, and their impact on humoral immunity in older adults.** At a minimum, this proposal will fill the knowledge

gap by examining whether the higher immunogenicity of these vaccines is a result of greater activation/suppression of genes/genesets (mRNA and miRNA) previously associated with immune responses to SDFlu, or additional unsuspected genes/genesets controlling immune responses.

**C. Knowledge Gap—Sex-Based Differences in Immune Responses to Influenza Vaccines.** Studies of **Multiple vaccines** (influenza, yellow fever, MMR, hepatitis A and B, herpes simplex [HSV] 2, rabies, smallpox, and dengue) demonstrate significantly higher Ab responses in females than males, as reported in a series of high-quality papers. Sex-based differences in humoral immune responses are observed prior to puberty, during the reproductive years, and after reproductive senescence, suggesting that sex hormones are not the necessary—or sole—mediators of sex differences in humoral immune responses to vaccines. **Despite significant evidence of immune response differences between the sexes, most vaccine studies do not analyze immune response outcome data by sex.**

Across a cohort of 556 older (ages 50–64) and 558 younger (ages 18–49) subjects, the SDFlu vaccine induced >1.5-fold higher A/H3N2-specific HAI Ab titers in women than men. Similarly, a study of SDFlu and HDFlu vaccine responses in 414 elderly subjects (ages 65–95) demonstrated higher rates of seroconversion in females than in males ( $p<0.05$ ). However, no significant differences in Ab measures were found in cohorts of 494 and 158 older adults after receiving SDFlu, and sex was also not reliably associated with seroprotection and/or Ab titers in children and young adults receiving MF59Flu. **These publications demonstrate inconsistent—and sometimes conflicting—findings regarding sex-based effects on immune responses to influenza vaccine.** Further research is needed, which is a stated priority for NIH research.

Additionally, new vaccines containing the MF59 adjuvant are likely to alter the transcriptomic signatures associated with vaccine responses in elderly populations, and potentially alter the influence of sex on those responses. The current lack of knowledge is a critical barrier to understanding poor vaccine responses in the elderly, and such knowledge is foundational to the future development of new influenza vaccines.

**D. Impact of this Work.** Given the substantially diminished efficacy of influenza vaccines with age and the importance of developing improved influenza vaccines, data from our studies could be used to inform directed and rational development of next-generation influenza vaccines and/or therapeutics—although the development of such a vaccine is not the purpose of this proposal. Age-related immune dysfunction (immunosenescence) might be overcome by adjuvant stimulation of innate and/or Th cell-specific genes, which may be different in males and females (see Expected Results). For example, a TLR4 agonist GLA-SE has been shown to enhance Th1 responses to influenza vaccine in older adults. The identification of critical chemokine pathways involving CCR5 and its ligands (CCL5) (see Preliminary Data #7), predictive of influenza vaccine-induced humoral immunity, may support the usage of CCR5 small molecule agonists/antagonists approaches in vaccines to modulate inflammatory response and T cell chemotaxis/activation for optimal Ab response.

## Study Design and Methods

### Methods:

#### Subject Recruitment, Enrollment and Screening

We will screen and recruit 400 generally healthy males and females ages 65 and older who meet all inclusion and exclusion criteria and are willing to receive a flu vaccine.

We will also screen and recruit 20 generally healthy males and females ages 18-40 as a control group. These subjects will only have a baseline blood draw (no flu vaccine administration and no follow-study visits).

Eligible subjects who consent and enroll into the study will undergo a baseline blood draw (up to 108 mL) and then be randomly assigned to receive either the MF59 (Fluad) flu vaccine (N=200) or the High Dose (Fluzone) flu vaccine (N=200). Subjects in the control group will undergo the baseline blood draw only (up to 108 mL). They will NOT receive a flu vaccine. The following sections describe the remaining study visits for the subjects who are ages 65 and older.

Subjects will then be asked to come back for three additional blood draws after their flu vaccination: Day 1, Day 8, and Day 28 after vaccination. Each blood draw will be up to 105mL of blood.

Flu vaccination can occur up to 2 weeks after the baseline blood draw. The Day 1 blood draw will occur the following day after vaccination. The Day 8 blood draw will occur 7-10 days after the vaccination. The Day 28 blood draw will occur 25-31 days after vaccination.

During the Baseline visit we will collect patient demographic information, height, weight, BMI, medication history, medical information, and information on alcohol and smoking use. Patients will also be offered the CDC's influenza vaccine-specific Vaccine Information Sheet that is routinely provided to Mayo patients.

During the 3 follow-up visits we will collect weight, medication history and medical information.

Subjects will be remunerated \$40 for each blood draw visit they complete.

We will also mail subjects, roughly a year after participation, 3 different sleep questionnaires as a way to assess sleep hygiene and immune response.

**Resources:** Potential participants will be identified through routine clinical appointments, advertising with flyers, brochures, an EMR search to identify mail-merge candidates, and existing lists/databases of individuals interested in being contacted about participation in research studies. Subject recruitment and advertisement will occur on Mayo campus and at various sites off campus (e.g., retirement centers). Permission will be obtained from each location before recruitment begins. We will also use newspaper and social media advertisements.

Based on a 2016 census by the United States Government, there were between 30,447 - 54,748 people 65 years of age or older in Olmsted County.

This project has been funded through the NIH through an R01 award.

The majority of the laboratory assays will be performed in the Vaccine Research Group Laboratory which occupies approximately 3,500 square feet on the sixth floor of the Mayo Clinic Guggenheim Research Building. Equipment not in this laboratory is readily available in institutional core laboratories and is freely shared.

(1a) This is a multisite study involving Mayo Clinic and non Mayo Clinic sites. *When checked, describe in detail the research procedures or activities that will be conducted by Mayo Clinic study staff.*

(1b) Mayo Clinic study staff will be engaged in research activity at a non Mayo Clinic site. *When checked, provide a detailed description of the activity that will be conducted by Mayo Clinic study staff.*

